- 12. Pharmacokinetic sampling at select sites for subjects in the control and treatment holiday groups; subjects in the treatment holiday group can have PK sampling performed at any time during the visit between Weeks 0 and 16. Otherwise, if on a dosing day, sampling must be performed **prior** to dosing. Collect blood samples pre-dose and post-dose at the end of the infusion at Weeks 24 and 52 (or earlier if belimumab is re-started before Week 24 in the event of a severe flare by using the escape option). Subjects in the long-term discontinuation group will have one PK sampling performed at any time during the visit between Weeks 0 and 24. PK sampling for the long-term discontinuation group is not performed after Week 24. Long-term discontinuation subjects withdrawing before Week 24 will have one PK sampling performed at any time during the EXIT visit. PK sampling for long-term discontinuation subjects withdrawing after Week 24 is not performed at the EXIT visit.
- 13. Blood sample for immunogenicity will be taken at Weeks 12, 24, 36 and 52 for all three groups. In addition, a blood sample for immunogenicity will also be taken 4 weeks prior to the reintroduction of belimumab (at Week 20 since belimumab will be reintroduced at Week 24) in the treatment holiday group. A blood sample for immunogenicity must be taken at least 6 months after the final dose of investigational product for any subjects in the control group or treatment holiday group who had an anti-belimumab antibody response at the 16-week follow-up visit (or at the last immunogenicity assessment if 16-week follow-up is not available). Note that serum samples for immunogenicity must be collected pre-dose at the time of dosing from subjects in the treatment holiday group who experience a severe flare prior to Week 24 and consequently receive open-label belimumab as rescue. Immunogenicity blood sample will not be collected at the 6-month follow up visit for subjects in the long-term discontinuation group as this visit does not apply to this subject group.
- 14. Measured in treatment holiday group at Weeks 16 and pre-dose at Week 24. Measured in long-term discontinuation group at Weeks 16, 24 and 32. Not measured in control group.

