8.4.2. Summary Measure

8.4.2.1. Immunogenicity

Immunogenic response will be summarized by visit and anytime postbaseline for the 52-week treatment phase.

Categories of response are Negative, Transient Positive (defined as a single positive response that does not occur at the final assessment, or Persistent Positive (defined as a positive response that occurs on at least 2 consecutive assessments or a single result at the final assessment).

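### Anti-drug antibody categories rest on consecutive samples, but only the treatment holiday group is sampled at Week 20, so the same antibody course can get different labels by group, and some non-consecutive positives fit no category

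*SAP*

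**What the plan says.** SAP 8.4.2.1 uses three categories: Negative, "Transient Positive (defined as a single positive response that does not occur at the final assessment", and "Persistent Positive (defined as a positive response that occurs on at least 2 consecutive assessments or a single result at the final assessment". It gives no minimum time between consecutive assessments. On scope it says: "Immunogenic response will be summarized by visit and anytime postbaseline for the 52-week treatment phase". SAP 2.2 lists the three categories, by visit and across all visits, as a secondary endpoint. SAP 8.4.4.1 uses observed data without imputation.

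The sampling schedule is in protocol Table 2, footnote 13, and is repeated in SAP 13.2.2. It says "Blood sample for immunogenicity will be taken at Weeks 12, 24, 36 and 52 for all three groups" and adds that "a blood sample for immunogenicity will also be taken 4 weeks prior to the reintroduction of belimumab (at Week 20". Only TH subjects give this extra sample. For early re-start after a severe flare it adds that "serum samples for immunogenicity must be collected pre-dose at the time of dosing from subjects in the treatment holiday group". The LTD group has the control schedule.

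The protocol's own endpoint (section 6.1.2) is the number of subjects with confirmed positive antibodies by the end of the study. It does not separate transient from persistent responses.

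**The concern.** A label based on consecutive samples is comparable between groups only if the groups are sampled at the same times. Here, consecutive can mean 4 weeks apart in TH (Weeks 20 and 24) but never less than 12 weeks apart in control and LTD. Nothing in SAP 2.2, 8.4 or the data-handling appendices, or in protocol 6.4.16, leaves Week 20 out of the classification or aligns the schedules.

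The categories also do not cover every result. A subject with two positives that are neither adjacent nor at the final assessment meets no definition, so whoever programs the table must decide.

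Protocol 1.2 names immunogenicity among the effects of withdrawal and reintroduction to be studied. With no test or adjustment planned, the displayed counts are the result. SAP 2.3 reports 12 TH and 29 control subjects enrolled, so one relabelled TH subject moves the TH percentage by 1/12 = 8.3 points.

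**Working it through.** The plan states no figure for this endpoint, so there is none to reproduce. I applied the SAP 8.4.2.1 rule to both schedules, assuming that all planned samples are taken and that Week 52 is the final assessment.

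**1. Same course, different labels.** These are the TH result patterns whose label changes when the Week 20 sample is absent, if any positive at Week 52 is read as Persistent:

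| Positive at weeks (TH) | Label in TH | Label on 12/24/36/52 |
|---|---|---|
| 20, 24 | Persistent | Transient |
| 12, 20 | Persistent | Transient |
| 20 | Transient | Negative |
| 12, 24 (20 negative) | none | Persistent |
| 20, 36 | none | Transient |
| 12, 20, 36 | Persistent | none |

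The first three rows are what a single continuous response can produce, and in each the TH label is higher. Rows four to six need a fluctuating response. In row four the extra sample takes a TH subject out of Persistent.

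**2. Size for one continuous response.** A response of D weeks starting at week s is positive at visit t when t − D ≤ s ≤ t. It is positive at both t1 and t2 when t2 − D ≤ s ≤ t1. The onsets that give two consecutive positives are:

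- D = 8: TH 16–20, 4 weeks; control none.
- D = 12: TH 8–20, 12 weeks; control none (only the single point s = 12 or s = 24).
- D = 16: TH 4–24, 20 weeks; control 8–12 and 20–24, 8 weeks.

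With onset uniform over Weeks 0–28, divide by 28. With onset uniform over Weeks 0–52, add the D weeks of onset that are positive at Week 52 (Persistent in both groups) and divide by 52.

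| D (weeks) | Onset 0–28, TH vs control | Onset 0–52, TH vs control |
|---|---|---|
| 8 | 4/28 = 14% vs 0% | 12/52 = 23% vs 8/52 = 15% |
| 12 | 12/28 = 43% vs 0% | 24/52 = 46% vs 12/52 = 23% |
| 16 | 20/28 = 71% vs 8/28 = 29% | 36/52 = 69% vs 24/52 = 46% |

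In both columns TH exceeds control by the same 4, 12 and 12 weeks of onset; only the denominator changes. Restricting to responses that start and end within the 52 weeks gives 4/44 = 9% vs 0%, 12/40 = 30% vs 0%, and 20/36 = 56% vs 8/36 = 22%.

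**3. Any positive at all.** An 8-week response is detected in 20/28 = 71% of TH vs 16/28 = 57% of control subjects (onset 0–28), or 36/52 = 69% vs 32/52 = 62% (onset 0–52). For 12- and 16-week responses over Weeks 0–52, detection is equal: 48/52 = 92% in both groups, and 100% in both.

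**4. Results with no category.** There are 2^5 − 1 = 31 non-negative patterns in TH and 2^4 − 1 = 15 in control/LTD.

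- If any positive at Week 52 counts as Persistent, the unclassified patterns are 12+24, 12+36 and 20+36 in TH (3 of 31) and 12+36 in control/LTD (1 of 15).
- If the final-assessment clause is read literally, as a lone positive at the final visit, then 12+52, 20+52, 24+52 and 12+24+52 join them in TH (7 of 31), and 12+52 and 24+52 join in control/LTD (3 of 15).

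These are counts of possible patterns, not expected numbers of subjects.

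**The case against.** The strongest case is that little depends on this. The study is descriptive, the protocol endpoint does not use the split, and every result appears in Listing 47. That stands as a limit on the consequence. It does not make the displayed categories comparable, and Week 20 still gives TH one more chance of a positive in the simple count.

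The size is open to dispute, and fairly. The contrasts with 0% come from restricting onset to Weeks 0–28 or to responses completed by Week 52. Letting onset run to Week 52 brings in control subjects who are Persistent through the final-assessment clause, and the difference between groups falls by about half.

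SAP 13.4.1.1 splits TH immunogenicity into holiday and re-start phases, and the calculation above treats it as one stream. SAP 8.4.2.1 refers to the 52-week phase, which supports one stream. If the rule were applied within phase, the pattern counts would change. The mislabelling would remain: SAP 13.4.1 puts an assessment on the cut-point date in the earlier phase, so Weeks 12, 20 and 24 stay together.

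A reader might also infer that antibody-positive subjects vanish from Table 3.51. The documents do not show this. The shells are not in the SAP, and results by visit would still be displayed. What is undefined is the across-visit label.

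**Conclusion.** Two defects are established from the text alone. The label depends on the group's sampling schedule whenever a response is seen at Week 20 but not on enough other visits to fix its category. The three categories also leave some positive results unassigned: 3 of 31 patterns in TH and 1 of 15 in control/LTD, or 7 and 3 on the literal reading.

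The size of the group difference is not established. It rests on assumed duration and onset. For responses of 8 to 16 weeks, the TH excess in Persistent is 4/28 to 12/28 (14 to 43 points) with onset over Weeks 0–28, and 4/52 to 12/52 (8 to 23 points) over Weeks 0–52.

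A reader might conclude that the definition always makes a holiday look more immunogenic. The documents do not support that. It holds for a single continuous response, but a fluctuating one can go the other way. Nor do they state as a secondary objective whether a holiday raises immunogenicity: protocol 2.2 says only that immunogenicity will be assessed.

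The SAP text should be corrected. The primary flare analysis is unaffected.

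**What to change.** In SAP 8.4.2.1:

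1. For the between-group across-visit categories and the any-time-positive count, use only the common post-baseline visits (Weeks 12, 24, 36 and 52) in all three groups.
2. Show the TH Week 20 results and the early re-start pre-dose results as separate rows of the table and in Listing 47.
3. Make the categories exhaustive. One way is Persistent = two or more positives, or positive at the final assessment; Transient = any other positive. This leaves no pattern unclassified on either schedule. A separate category for intermittent positives would also close the gap; what matters is that the assignment is stated.

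The cost is SAP wording and a small derivation change, with no new samples. There are two drawbacks. A TH response seen only at Week 20 is shown outside the between-group categories. The revised Persistent wording may also differ from the programme-standard display, which is how the SAP marks Table 3.51, so the difference should be footnoted.

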8.4.2.2. Vital signs

Change from baseline in vital signs will be presented using summary statistics by visit.

Baseline body mass index (BMI) will be calculated from weight and height measurements.

$$BMI (kg/m^2) = \frac{Weight (kg)}{[Height (m)]^2}$$

BMI will be derived at each visit using the baseline value for height and the weight at the visit. Since height is collected in centimeters (cm), it will be converted to meters (m) by dividing by 100 before using it in the formula above.

8.4.3. Population of Interest

For immunogenicity and vital signs endpoints, the analyses will be based on the ITT population.

8.4.4. Strategy for Intercurrent (Post-Randomization) Events

8.4.4.1. Immunogenicity

Observed data will be used with no imputation.

8.4.4.2. Vital signs

Observed data will be used with no imputation. If weight or height is missing, then BMI will be missing.

8.4.5. Statistical Analyses / Methods

Details of the planned displays are provided in Appendix 11: List of Data Displays and will be based on GSK data standards and statistical principles.

Unless otherwise specified, endpoints / variables defined in Section 8.4.1 will be summarised using descriptive statistics, graphically presented (where appropriate) and listed.

8.5. Safety Data for Maintenance Phase Subject Profile

AE data, grade 3 or 4 laboratory data, and immunogenicity data will be listed on the subject profile.

9. PHARMACOKINETIC ANALYSES

9.1. Primary Pharmacokinetic Analyses

The primary PK analysis will be of the serum belimumab concentrations.

9.1.1. Endpoint / Variables

Refer Section 13.5.3 Reporting Standards for Pharmacokinetic.

9.1.2. Summary Measure

Descriptive statistics for serum belimumab concentrations will be displayed for each visit. The tables will display the mean value, standard deviation, 95% CI of mean, geometric mean, % CV, 95% CI of geometric mean, median, 25th and 75th percentiles, minimum and maximum.

9.1.3. Population of Interest

The primary pharmacokinetic analyses will be based on the PK population, unless otherwise specified.

9.1.4. Strategy for Intercurrent (Post-Randomization) Events

Observed data will be used with no imputation.

9.1.5. Statistical Analyses / Methods

Details of the planned displays are provided in Appendix 11: List of Data Displays and will be based on GSK data standards and statistical principles.

Unless otherwise specified, endpoints / variables defined in Section 9.1.1 will be summarised using descriptive statistics, graphically presented (where appropriate) and listed.

10. POPULATION PHARMACOKINETIC (POPPK) ANALYSES

Population Pharmacokinetic Analysis are not applicable to this study.

11. BIOMARKER ANALYSES

11.1. Primary Biomarker Analyses

11.1.1. Endpoint / Variables

Autoantibodies (anti-dsDNA, ANA), BLyS protein, B-cells (CD19+, CD20+, CD20+/27+ memory, CD20+/27-naïve, CD20+/69+activated, CD20+/138+plasmacytoid, CD19+/27BRIGHT/38BRIGHT SLE subset and CD20-/138+ plasma cells), immunoglobulins (IgG, IgA, and IgM), and complement (C3 and C4) will be assessed. See Section 13.6.6.2 for additional details.

11.1.2. Summary Measure

11.1.2.1. B-Cells

For the B-cells, the change and percent change from baseline in the original parent study will be summarized at Weeks 0, 8, 16, 24, 32, 40 and 52 and from Week 24 to 32, Week 24 to 40, and Week 24 to 52.

11.1.2.2. Autoantibodies, Immunoglobulins and Complement

For autoantibodies, immunoglobulins and complement, the change and percent change from baseline in the original parent study to each visit including the Day 0 visit in the 52-week treatment phase will be assessed.

Shifts from baseline in IgG, IgM, IgA, anti-dsDNA, ANA, C3 and C4.

11.1.2.3. BLyS Protein

The change and percent change from baseline in the original parent study to each visit in the 52-week treatment phase will be assessed.

11.1.3. Population of Interest

For all endpoints in Section 11.1.1, the primary biomarker analyses will be based on the ITT population.

11.1.4. Strategy for Intercurrent (Post-Randomization) Events

For all endpoints in Section 11.1.1, observed data will be used with no imputation.

11.1.5. Statistical Analyses / Methods

Details of the planned displays are provided in Appendix 11: List of Data Displays and will be based on GSK Data Standards and statistical principles.

Unless otherwise specified, endpoints / variables defined in Section 11.1.1 will be summarised using descriptive statistics, graphically presented (where appropriate) and listed.

13. APPENDICES

13.1. Appendix 1: Protocol Deviation

See Section 4.1 for details.

13.2. Appendix 2: Schedule of Activities

13.2.1. Protocol Defined Schedule of Events

13.2.2. Time and Events Table (Year 1)

	Screen						T	reatmen	t Holida	y Study	1					Follo	w-up
Visit	1	2	3	4	5	6	7	8	9	10	11	12	13	14	15		
Study Day	Up to -30 ¹	0 ²	28 ±7d	56 ±7d	84 ±7d	112 ±7d	140± 7d	168 ±7d	196± 7d	224 ±7d	252 ±7d	280± 7d	308 ±7d	336 ±7d	364 ±7d or Exit	16-wk ±7d ³	6 mo ±7d
Study Week		0	4	8	12	16	20	24	28	32	36	40	44	48	52		
Written Informed Consent ⁴	Х																
Demography		Х															
Medical History		Х															
SLE History		Х															
Therapy History		Х															
Physical Examination		Х															
Inclusion/Exclusion		Х															
Efficacy Assessments				-		-	-	-					-	-	-	-	
DAS: SS, SLE Flare Index, PGA ⁵	X 1	Х	Х	Х	Х	Х	Х	Х	Х	Х	Х	Х	Х	Х	Х		
SLICC/ACR Damage Index		Х						Х							Х		
Safety Assessments																	
Vital Signs ⁶		Х	Х	Х	Х	Х	Х	Х	Х	Х	Х	Х	Х	Х	Х	Х	
Weight, height ^{6, 7}		Х	Х	Х	Х	Х	Х	Х	Х	Х	Х	Х	Х	Х	Х		
Symptom-driven Physical Exam		Х	Х	Х	Х	Х	Х	Х	Х	Х	х	Х	Х	Х	Х	Х	
Record Concurrent																	
Medications		Х	Х	Х	X	Х	Х	Х	Х	Х	Х	Х	Х	Х	Х	Х	
Adverse Events		Х	Х	Х	Х	Х	Х	Х	Х	Х	Х	Х	Х	Х	Х	Х	
Laboratory Assessments																	
Haematology & Modified Chem 20 (non-fasting) ⁶	Х	Х	Х	Х	Х	Х	Х	Х	Х	Х	Х	Х	Х	Х	х	Х	
Urinalysis	Х	Х	Х	Х	Х	Х	Х	Х	Х	Х	Х	Х	Х	Х	Х	Х	
Spot urine (protein to	Х	Х	Х	Х	Х	Х	Х	Х	Х	Х	Х	Х	Х	Х	Х		

2018N381035_00

BEL116027

	Screen						Т	reatmer	t Holida	y Study	1					Follo	w-up
Visit	1	2	3	4	5	6	7	8	9	10	11	12	13	14	15		
Study Day	Up to -30 ¹	0 ²	28 ±7d	56 ±7d	84 ±7d	112 ±7d	140± 7d	168 ±7d	196± 7d	224 ±7d	252 ±7d	280± 7d	308 ±7d	336 ±7d	364 ±7d or Exit	16-wk ±7d ³	6 mo ±7d
Study Week		0	4	8	12	16	20	24	28	32	36	40	44	48	52		
creatinine ratio) 8																	
Pregnancy Test 6, 9	U	U	U	U	U	U	U	U	U	U	U	U	U	U	U	U	
Pharmacogenetic Sampling ¹⁰		Х															
aCL Autoantibody		Х													Х		
C3/C4	Х	Х	Х	Х	Х	Х	Х	Х	Х	Х	Х	Х	Х	Х	Х		
Anti-dsDNA Autoantibodies	Х	Х	Х	Х	Х	Х	Х	Х	Х	Х	Х	Х	Х	Х	Х		
ANA Autoantibodies		Х						Х							Х		
IgG, IgA & IgM ¹¹		Х		Х		Х		Х		Х		Х		Х	Х		
PT/ PTT		Х															
Exploratory Lab Assessments	5																
Pharmacokinetic Sampling ¹²		Х		Х		Х		X 12		Х					X 12		
Immunogenicity ^{6, 13}		Х			Х		X 13	Х			Х				Х	Х	X 13
BLyS Protein 14						Х		Х		Х							
B cell Markers ¹⁵		Х		Х		Х		Х		Х		Х			Х		Х
Investigational Product (IP)																	
IP Administration ¹⁶		Х	Х	Х	Х	Х	Х	Х	Х	Х	Х	Х	Х	Х	X		

1. DAS = disease activity scales; SS = SELENA SLEDAI; SLE = systemic Lupus Erythematosus; PGA = Physician's Global Assessment; SLICC/ACR = Systemic Lupus International Collaborating Clinics/American College of Rheumatology; ALT = alanine aminotransaminase; AST = aspartate aminotransaminase; PT/PTT = prothrombin time/partial thromboplastin time; BlyS = B Lymphocyte Stimulator; IP = investigational product; aCL = anticardiolipin

2. A screening visit of up to 30 days prior to the Day 0 visit will be scheduled for subjects in the treatment holiday and control groups for assessment of SELENA SLEDAI score to assess eligibility.

- 3. The EXIT Visit in the respective feeder continuation studies will serve as the Day 0 visit for all 3 subject groups in this study. Assessments covered for both this study at Day 0 and the Exit visit of the feeder continuation studies need only be performed once and recorded in the appropriate case report forms for each study. Subjects in the control group must be able to receive the 1st dose of belimumab on Day 0 of this study on average 4 weeks (minimum of 2 weeks, maximum of 8 weeks) after the last dose in the feeder continuation study.
- 4. The 16 week follow-up visit will occur at approximately 16 weeks after last dose of investigational product for subjects in the control group who withdraw at any time during the study, or for subjects in the treatment holiday group who withdraw from the study from Week 24 onwards (Visit 7) during the belimumab re-introduction period. The 16-week and 6 month follow-up visits do not apply to subjects in the long-term discontinuation group.
- 5. Obtain written informed consent to participate in this study at the Screening visit.

- 6. Guidelines for scoring proteinuria for SELENA SLEDAI are provided in protocol Section 6.3.1.1.
- 7. Complete assessment prior to belimumab dosing for subjects in the control group (to Week 48) and for subjects in the treatment holiday group (during Weeks 24 to 48 or earlier in the event of a flare). Immunogenicity testing includes quantifying the amount of belimumab present in the samples using the belimumab PK assay.
- 8. For any subject whose weight changes by more than 5% from that recorded at Day 0, use the weight at the current visit for calculating the belimumab dose to be administered. Height measured only at Day 0.
- 9. A 24-hour urine may be done as an additional assessment if clinically indicated (e.g., renal flare).
- 10. Urine pregnancy test results for women of child-bearing potential must be available prior to dosing (during Weeks 0 to 48 in the control group and during Weeks 24 to 48 or earlier in the event of a flare in the treatment holiday group). Can be performed at any time during the visit for females of child-bearing potential in the long-term discontinuation group.
- 11. PGx sampling from consenting subjects recruited from all studies except from study BEL114333. PGx informed consent must be obtained prior to sampling.
- 12. Serum immunoglobulin isotypes: IgG, IgM, IgA.
- 13. Pharmacokinetic sampling at select sites for subjects in the control and treatment holiday groups; subjects in the treatment holiday group can have PK sampling performed at any time during the visit between Weeks 0 and 16. Otherwise, if on a dosing day, sampling must be performed **prior** to dosing. Collect blood samples pre-dose and post-dose at the end of the infusion at Weeks 24 and 52 (or earlier if belimumab is re-started before Week 24 in the event of a severe flare by using the escape option). Subjects in the long-term discontinuation group will have one PK sampling performed at any time during the visit between Weeks 0 and 24. PK sampling for the long-term discontinuation group is not performed after Week 24. Long-term discontinuation subjects withdrawing before Week 24 will have one PK sampling performed at any time during the EXIT visit. PK sampling for long-term discontinuation subjects withdrawing after Week 24 is not performed at the EXIT visit.
- 14. Blood sample for immunogenicity will be taken at Weeks 12, 24, 36 and 52 for all three groups. In addition, a blood sample for immunogenicity will also be taken **4 weeks prior** to the reintroduction of belimumab (at Week 20 since belimumab will be reintroduced at Week 24) in the treatment holiday group. A blood sample for immunogenicity must be taken at least 6 months after the final dose of investigational product for any subjects in the control group or treatment holiday group who had an anti-belimumab antibody response at the 16-week follow-up visit (or at the last immunogenicity assessment if 16-week follow-up is not available). **Note** that serum samples for immunogenicity must be collected pre-dose at the time of dosing from subjects in the treatment holiday group who experience a severe flare prior to Week 24 and consequently receive open-label belimumab as rescue. Immunogenicity blood sample will not be collected at the 6-month follow up visit for subjects in the long-term discontinuation group as this visit does not apply to this subject group.
- 15. Measured in treatment holiday group at Weeks 16 and pre-dose at Week 24. Measured in long-term discontinuation group at Weeks 16, 24 and 32. Not measured in control group.
- 16. Biological Markers include FACS of peripheral lymphocytes: B lymphocytes (CD20+, CD20+/27+ memory, CD20+/27- naïve, CD20+/69+ activated, CD20+/138+ plasmacytoid, CD19+/27^{BRIGHT}/38^{BRIGHT} SLE subset and CD20-/138+ plasma cells). Note: B cell markers will not be collected at the 6-month follow up visit for subjects in the long-term discontinuation group as this visit does not apply to this subject group.
- 17. Only subjects in the control group will receive belimumab 10 mg/kg during Weeks 0 through 20 inclusive; subjects in the control group must be able to receive the first dose of belimumab in this study 4 weeks (minimum of 2 weeks, maximum of 8 weeks) after the last dose in their previous open-label continuation study Subjects in the control group and treatment holiday groups will receive belimumab from Weeks 24 through 48 although subjects in the treatment holiday group may be treated with belimumab prior to Week 24 as determined by the investigator in the event of increased SLE activity. When belimumab therapy is re-started, subjects in the treatment holiday group will remain under clinical supervision for 3 hours after completion of the first 2 infusions. At the Week 52 visit, only subjects in the treatment holiday and control groups who are continuing belimumab therapy beyond this time will be dosed.

2018N381035_00 BEL116027

